The distributions of OS, PFS, and time to progression to AML will be compared using a stratified log rank test for the ITT population. The Kaplan-Meier method will be used to estimate the distribution for each treatment. The treatment effect (hazard ratio) and its 2-sided 95% confidence intervals are to be estimated using a stratified Cox regression model with treatment as the sole explanatory variable. The reasons of censoring in time to progression to AML will be tabulated.

The time to 8-week and 24-week RBC TI will be summarized descriptively based on ITT 8-week and 24-week RBC TI responders, respectively. The Kaplan-Meier method will be used to estimate the distribution of duration of RBC TI based on ITT 8-week and 24-week RBC TI responders, respectively.

The amount and relative change in RBC transfusions will be summarized descriptively by treatment by time point.

Change from baseline in scores from QUALMS, FACT-An, and EQ-5D-5L will be summarized descriptively by treatment group. The PRO measure of interest and analysis methods (eg, responder analysis, longitudinal analysis with repeated measures) will be specified in the Statistical Analysis Plan.

A sequential gate-keeping procedure will be implemented to ensure that the overall type I error rate for the secondary endpoints is controlled. Details of selected secondary endpoints to be tested

and the testing procedure will be specified in the Statistical Analysis Plan.

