Progression free survival, defined as the time interval from Study Day 1 to the first date of disease progression or death from any cause, whichever occurs first. Subjects who received subsequent anti-cancer therapy prior to documented progression will be censored at the date of last evaluable response assessment or disease progression status conducted on or prior to the initiation of subsequent anti-cancer therapy. If subjects do not have any adequate post-baseline assessment and did not die, PFS will be censored at Study Day 1.

PFS will be computed as date of PFS event or censoring – Study Day 1+ 1.

Overall Survival (OS)

OS is defined as the interval from Study Day 1 to death from any cause. Survival time of living subjects will be censored on the last date a subject is known to be alive or lost to follow-up.

Time to progression to AML

Time to progression to AML is defined as the interval from Study Day 1 to the date of AML progression. Subjects who received subsequent anti-cancer therapy prior to documented progression will be censored at the date of last evaluable response assessment or disease progression status conducted on or prior to the initiation of subsequent anti-cancer therapy. If subjects do not have any adequate post-baseline assessment, time to progression to AML will be censored at Study Day 1.

Amount and relative change in RBC transfusions

Amount of RBC transfusions per 8-week (16-week) is defined as the total number of RBC transfusion units in a given 8-week (16-week) interval during study.

Relative change in RBC transfusions per 8-week = (amount of RBC transfusions per 8-week – prior RBC transfusion burden) / prior RBC transfusion burden multiply by 100%.

Relative change in RBC transfusions per 16-week = (amount of RBC transfusions per 16-week – total RBC transfusion units in 16 weeks prior to study entry) / total RBC transfusion burden in 16 weeks prior to study entry multiply by 100%.

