4.9.3.2 Analysis Methods

Part 1 (Phase 2):

The proportion of subjects with 24-week RBC TI, CR, PR, and hematologic improvement, and other binary endpoints, will be summarized with percentage along with its 95% 2-sided exact Clopper-Pearson CI. The time to 8-week RBC TI and time to 24-week RBC TI will be summarized descriptively based on 8-week and 24-week TI responder analysis set, respectively. The Kaplan-Meier method will be used to estimate the distribution of duration of RBC TI based on 8-week and 24-week TI responder analysis set, respectively. The distribution of OS, PFS, and time to progression to AML will be summarized using similar Kaplan-Meier methods.

Part 2 (Phase 3):

The 24-week RBC TI rates will be summarized with frequencies and percentages along with 2-sided 95% exact Clopper-Pearson CIs for the 2 treatment groups. Difference in TI and its 95% CI will be presented using Wilson Score method [1]. The comparison will be based on a stratified CMH test adjusting for the stratification factors at a two-sided significant level of 0.05.

Sensitivity analyses will be performed for Part 2 to evaluate the robustness of the 24-week RBC TI endpoint and includes:

- CMH test of 24-week RBC TI based on MITT analysis set in the case there are subjects who were dosed, but didn't receive any assigned treatment;
- CMH test of 24-week RBC TI based on per-protocol analysis set;

The time to 8-week and 24-week RBC TI will be summarized descriptively for the 2 treatment groups based on ITT 8-week and 24-week TI responder analysis set, respectively. The Kaplan-Meier method will be used to estimate the distribution of duration of RBC TI based on ITT 8-week and 24-week TI responder analysis set, respectively, and will be compared between two treatment groups using stratified log rank test based on ITT 8-week responder analysis set. The distribution of cumulative duration of RBC TI ≥ 8 weeks (sum of all durations of RBC TI ≥ 8 weeks) will be estimated by Kaplan-Meier based on ITT 8-week responder analysis set as well.

The proportion of subjects with hematologic improvement, CR, PR, or mCR per modified IWG 2006, and other binary endpoints will be evaluated using the same statistical methods as for the endpoint of 24-week RBC TI rates. The 8-week RBC TI rate in the first 24 weeks and 48 weeks (proportion of subjects who had RBC TI ≥ 8 weeks in the first 24/48 weeks) will be evaluated similarly.

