The distribution of OS, PFS, and time to progression to AML will be compared using stratified log rank test for ITT analysis set. The Kaplan-Meier method will be used to estimate the

distribution for each treatment. The treatment effect (hazard ratio) and its two-sided 95% CIs are to be estimated using a stratified Cox regression model with treatment as the sole explanatory variable. The reasons for censoring of time to progression to AML will be tabulated.

For both Part 1 and 2, the amount and relative change in RBC transfusions will be summarized descriptively for each treatment group, and the relative and absolute change in transfusion amount in the best 8-week (16-week) interval (defined as an 8-week or 16-week interval where the subject had the fewest RBC transfusions on study) will be illustrated by waterfall plots. The distribution of duration from the start of the first 8-week interval that had ≥ 4 units of RBC transfusion reduction to the End of Treatment visit (or censored at the last dose day if still on treatment) will be estimated by the Kaplan-Meier method based on HI-E responders (transfusion reduction) for each treatment group.

Hemoglobin means, mean changes over time, and Hb rise (defined as the maximum Hb value in the longest transfusion free interval excluding values that were within 14 days after transfusion—the pretreatment Hb level) for subjects who achieved 8-week or 24-week RBC TI will be summarized for each treatment group. The longest transfusion free interval will be also illustrated by waterfall plots and swimmer-lane plots as appropriate.

Summary statistics (N, mean, SD, median, and range) and changes from baseline will be calculated for serum ferritin by scheduled visits for each treatment group. The usage of iron chelation therapy (ICT) will be summarized as well.

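### Time to AML is estimated in each arm only by Kaplan-Meier, and no rule covers a subject who is assessed, has no subsequent therapy and dies without AML; if these deaths are censored, the AML probability is somewhat overstated

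*SAP*

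**What the plan says.** Time to AML runs from Study Day 1 to AML, which is its only event (Protocol 9.2.2; SAP 4.9.3.1).

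**Estimator.** Kaplan-Meier is the only method for the distribution by arm. Protocol 11.4 states: "The Kaplan-Meier method will be used to estimate the distribution for each treatment". SAP 4.9.3.2 repeats this for Part 2, with a stratified log-rank test "for ITT analysis set. The Kaplan-Meier method will be used to estimate the" distribution in each arm, and for Part 1 it says: "The distribution of OS, PFS, and time to progression to AML will be summarized using similar Kaplan-Meier methods". Part 2 adds a stratified Cox model. Neither document plans a cumulative incidence or other competing-risk estimate.

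**Censoring.** Protocol 9.2.2 censors at the last disease evaluation those subjects who are AML-free and alive at the cutoff, or who withdraw. SAP 4.9.3.1 adds two rules:

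- Subsequent therapy: "Subjects who received subsequent anti-cancer therapy prior to documented progression will be censored at the date of last evaluable response assessment" (or disease progression status) on or before the start of that therapy.
- No usable follow-up: "If subjects do not have any adequate post-baseline assessment, time to progression to AML will be censored at Study Day 1".

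The matching PFS rule exempts deaths: "If subjects do not have any adequate post-baseline assessment and did not die, PFS will be censored at Study Day 1". The AML rule has no such exemption. SAP 4.9.3.2 also promises a table: "The reasons for censoring of time to progression to AML will be tabulated".

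**The concern.** A subject can die before AML develops. The two SAP rules reach some of these deaths: those after subsequent therapy, and those before any adequate assessment. A subject who was assessed, received no subsequent therapy and then died without AML falls under no rule in either document.

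Counting such a death as an event would contradict the endpoint's definition, so a programmer would most naturally censor it. One minus Kaplan-Meier then treats the dead as still able to develop AML. It estimates the AML risk as if nobody died first, which is higher than the proportion who actually progress. A reader of the curve, or of a percentage taken from it, would probably read it as the chance of AML. The planned table may show how many such deaths there were, but it does not correct the curve.

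**Working it through.** The documents give no AML probability, event count or power for this endpoint, so there is no stated figure to reproduce. The size is worked out from their background rates.

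**Inputs**
- Early ESA failure (Protocol 1.1.4): AML in 12-20% over 5 years; median survival about 3.5 years.
- IPSS low (Protocol 1.1.3): 25% AML at 9.4 years; median survival 5.7 years.
- IPSS intermediate-1 (Protocol 1.1.3): 25% AML at 3.3 years; median survival 3.5 years.
- Imetelstat arm: 115 subjects (SAP 4.12).

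**Formulas.** Constant hazards, a for AML and d for death without AML:
- 1-KM(t) = 1 - exp(-a t)
- CIF(t) = a/(a+d) × [1 - exp(-(a+d) t)]

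**Mortality assumptions**
- A: a + d = ln 2 / median survival, so AML is part of the total exit rate.
- B: d = ln 2 / median survival, so all mortality is AML-free.

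The documents do not say whether the quoted AML percentages are Kaplan-Meier or cumulative incidence figures, so each is read both ways.

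**Examples under A, early ESA failure** (ln 2/3.5 = 0.1980 per year)
- 12% read as 1-KM: a = -ln(0.88)/5 = 0.0256; d = 0.1980 - 0.0256 = 0.1725 (before rounding). Year 1: 2.52% against 2.32%, excess 0.20 points, ratio 1.09. Year 2: 4.98% against 4.22%, excess 0.76, ratio 1.18.
- 20% read as cumulative incidence: a = 0.20 × 0.1980/(1 - exp(-0.990)) = 0.0630; d = 0.1350. Year 1: 6.11% against 5.72%, excess 0.39, ratio 1.07. Year 2: 11.84% against 10.41%, excess 1.43, ratio 1.14.

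**Example under B.** 20% read as cumulative incidence, d = 0.1980: solving CIF(5) = 0.20 gives a = 0.0731. Year 1: 7.04% against 6.40%, excess 0.65 before rounding. Year 2: 13.6% against 11.3%, excess 2.3.

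**All cases** (ranges cover both readings; excess in percentage points)

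| Inputs | Assumption | 1 y ratio | 1 y excess | 2 y ratio | 2 y excess |
|---|---|---|---|---|---|
| Early ESA failure | A | 1.07-1.09 | 0.20-0.39 | 1.14-1.18 | 0.76-1.43 |
| Early ESA failure | B | 1.10 | 0.23-0.65 | 1.21 | 0.86-2.3 |
| IPSS low | A | 1.04-1.05 | 0.13-0.16 | 1.08-1.09 | 0.50-0.62 |
| IPSS low | B | 1.06 | 0.18-0.31 | 1.12-1.13 | 0.66-1.14 |
| Intermediate-1 | A | 1.05-1.06 | 0.44 | 1.09-1.11 | 1.6 |
| Intermediate-1 | B | 1.10 | 0.76-1.05 | 1.20 | 2.7-3.7 |

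**Against sampling error.** Binomial standard error, ignoring censoring, = sqrt(CIF(1-CIF)/115). At 2 years:
- Early ESA failure: the excess is 0.41-0.50 standard errors under A and at most 0.78 under B.
- Intermediate-1: 1.6/3.3 = about 0.5 under A; at most 3.65/3.59 = about 1.0 under B.

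**The case against.** The case against acting is that little depends on this curve. Time to AML is outside the tested sequence (SAP 4.9.1.3), no AML percentage at a fixed time is promised, PFS already counts death, and the reasons for censoring will be tabulated. The inputs are also borrowed: Protocol 1.1.4 describes early ESA failure only, and Protocol 1.1.3 gives figures by IPSS group. All-patient mortality is applied here to an endpoint that is censored at subsequent therapy. All of this stands and limits the size and weight of the point. It does not supply the missing rule or make 1-KM an estimate of AML probability.

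A reader might infer more than the documents support:

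- **That only the Study Day 1 rule reaches deaths without AML.** The subsequent-therapy rule also censors AML-free subjects who die later. Protocol 3.2 foresees placebo subjects stopping after unblinding, with later treatment recorded as subsequent therapy, so that group may not be small.
- **That ratios of 1.10 and 1.21 are the expected size.** They arise only if the whole mortality hazard is AML-free.
- **That the treatment comparison is biased.** Censoring deaths is correct for a cause-specific log-rank test and hazard ratio.
- **That the curve is wrongly compared with OS.** OS is not censored at subsequent therapy ("Survival time of living subjects will be censored on the last date a subject is known to be alive or lost to follow-up"), so the two are on different bases, but neither document plans to compare them.
- **That the Extension Phase analysis has the same fault.** Protocol 11 names no estimator for it, and the SAP is written to Amendment 7.

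**Conclusion.** The gap is real and narrow: assessed, no subsequent therapy, death without AML. If those deaths are censored, 1-KM overstates the AML probability in each arm. With constant hazards and the early-ESA-failure rates, the central estimate is 0.2 to 0.4 points at 1 year and 0.8 to 1.4 at 2 years, at most half a standard error in the larger arm. The least favourable case examined at 2 years, intermediate-1 rates with all mortality AML-free, gives 3.7 points, about one standard error. These figures are illustrative, because the death hazard before subsequent therapy in this population is not in the documents. The direction is firmer than the size. The point concerns only how the probability in each arm is described; alpha, power and the tested endpoints are untouched. It is a cheap improvement, worth making.

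**What to change.** In SAP 4.9.3.1 and 4.9.3.2 and Protocol 11.4:

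1. State that death without AML is a competing event for the probability in each arm, and a censoring event for the log-rank test and Cox model, both labelled cause-specific.
2. Add the Aalen-Johansen cumulative incidence of AML by arm, with death without AML alongside, and take AML percentages from it rather than from 1-KM. The Kaplan-Meier curve need not be removed.
3. Set one censoring-date convention for this estimate. Living subjects are now censored at the last disease evaluation. If deaths are counted at the death date, the risk set after the last evaluation over-represents those who die, which inflates the death curve and depresses the AML curve. Either count a death only within a stated window after the last evaluation, or follow living subjects to the last date on which AML status is known by contact. Report deaths before any adequate assessment separately, since AML status may be unknown.
4. Label the estimate *AML before subsequent therapy*, because the existing censoring rule makes it so.
5. Give death without AML its own row in the planned table of censoring reasons.

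The cost is some wording, a little programming and an agreed convention for the gap between last evaluation and death. Dates of death are already collected (Protocol 9.1.5).

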4.10 Safety Evaluation

All safety summaries and analyses will be based upon the Safety Analysis Set as defined in Section 4.5.2. Safety variables are to be tabulated by descriptive statistics (n, mean, median, standard deviation, minimum, and maximum; or n and percent). Missing safety data will generally not be imputed. As an exception, adverse events that have missing causality (after data querying) will be assumed to be related to study drug.

4.10.1 Adverse Events

The verbatim terms used in the eCRF by investigators to identify AEs will be coded using the latest version Medical Dictionary for Regulatory Activities (MedDRA). The severity of adverse events is assessed in NCI-CTCAE Version 4.03.

The safety parameters to be evaluated are the incidence, intensity, and type of adverse events, vital signs measurements, clinical laboratory results (hematology and chemistry), and deaths.

Drug-related AEs are those assessed by investigator as being possible, probable or very likely related to study drug.

Treatment-emergent AEs (TEAEs) will be summarized and are defined as those events that 1) occur after the first dose of study drug, through the treatment phase, and for 30 days following the last dose of study drug or until subsequent anti-cancer therapy if earlier; 2) any event that is considered study drug-related regardless of the start date of the event; or 3) any event that is presented at baseline but worsens in severity or is subsequently considered drug-related by the investigator.

TEAEs will be summarized by system organ class (SOC) and preferred terms (PT), by NCI CTCAE V4.03 grade, by relationship to study drug, and by action taken. For each TEAE, the percentage of subjects who experience ≥ 1 occurrence of the given event will be summarized. The same summary will be provided for serious TEAEs, and drug-related serious TEAEs, as well as TEAEs leading to treatment discontinuation, death, dose modifications or delays.

For each subject and each AE, the worst severity recorded will be attributed and used in the by-severity summaries. Similarly, the worst causality (most related to treatment) will be attributed and used in the by-causality summaries.

By-subject listings of all AEs (including non-treatment-emergent events), all serious AEs, all deaths that occurred during the study, all TEAEs leading to discontinuation or dose modification of study treatment will be provided. The listings will include: center, subject identifier, treatment group, age, sex, race, adverse event (SOC, PT, and verbatim term) and other information. Additional summaries, listings, subgroup analysis, or subject narratives may be provided, as appropriate.

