Subjects will be stratified in the randomization process according to prior RBC transfusion burden (≤ 6 or >6 units RBC) and by IPSS risk group (low versus intermediate-1) to ensure equal distribution across treatment groups. Prior RBC transfusion burden is defined as the maximum number of RBC units transfused over an 8-week period during the 16 weeks prior to C1D1 (Part 1) or Randomization (Part 2).

Blinded treatment will be used to minimize the potential influence of treatment assignment knowledge on clinical decision making, such as transfusion administration, and to reduce potential bias during data collection and evaluation of clinical endpoints; thus, ensuring the robustness and integrity of the study. The primary objective and secondary efficacy objectives of Part 2 of the main study are to compare RBC TI, time to RBC TI, and duration of RBC TI between the 2 treatment groups (imetelstat and placebo). The use of the modified IWG 2006 criteria to assess disease progression is intended to promote uniformity across study centers. It is the intent that all subjects, investigators, and study team members, except some required project roles (eg, members associated with DMC and HEC), will remain blinded to treatment group assignment at least until the primary efficacy analysis (12 months after the last subject is randomized in the main study of Part 2). As of Protocol Amendment 8, subjects, investigators, and study team members will be

unblinded after primary efficacy analysis. Upon unblinding the subjects after the primary analysis, subjects on imetelstat may continue treatment per investigator discretion. Subjects on placebo may discontinue treatment and enter the posttreatment follow-up phase of the study. The investigator will discuss treatment options with subject's discontinuing study treatment and record treatment selection as part of subsequent therapy.

Study Population

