5.2. Blinding and Unblinding

The investigator will not be provided with randomization codes. The codes will be maintained within the IWRS, which has the functionality to allow the investigator to break the blind for an individual subject.

Data that may potentially unblind the treatment assignment (ie, study drug plasma concentrations) will be handled with special care to ensure that the integrity of the blind is maintained and the potential for bias is minimized. This may include making special provisions, such as segregating

the data in question from view by the investigators, clinical team, or others as appropriate until the time of database lock and unblinding.

Under normal circumstances, the blind should not be broken until all subjects have completed the study and the database is finalized. Otherwise, the blind should be broken only if specific emergency treatment/course of action would be dictated by knowing the treatment status of the subject. In such cases, the investigator may in an emergency determine the identity of the treatment by contacting the IWRS. It is recommended that the investigator contact the sponsor or its designee if possible, to discuss the particular situation, before breaking the blind. Telephone contact with the sponsor or its designee will be available 24 hours per day, 7 days per week. In the event the blind is broken, the sponsor must be informed as soon as possible. The date, time, and reason for the unblinding must be documented by the IWRS, in the appropriate section of the case report form (CRF), and in the source document. The documentation received from the IWRS indicating the code break must be retained with the subject's source documents in a secure manner. Subjects who have had their treatment assignment unblinded should continue to return for scheduled evaluations and with sponsor approval may continue study drug. It is the intent that all subjects, investigators, and study team members, except some required project roles (eg, members associated with DMC and HEC), will remain blinded to treatment group assignment at least until the primary efficacy analysis (12 months after the last subject is randomized in the main study of Part 2). As of Protocol Amendment 8, subjects, investigators, and study team members will be unblinded after primary efficacy analysis.

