11.10. Safety Analyses

Safety analyses will be performed using the treated population. Safety will be evaluated using the National Cancer Institute Common Terminology Criteria for Adverse Events (NCI-CTCAE) (Version 4.03). The safety parameters to be evaluated are the incidence, intensity, and type of adverse events, clinically significant changes in the subject's physical examination findings, vital signs measurements, clinical laboratory results (hematology and chemistry), and deaths. Exposure to study drug and reasons for discontinuation will be tabulated. Safety variables are to be tabulated by descriptive statistics (n, mean, median, standard deviation, minimum, and maximum; or n and percent).

Adverse Events

Treatment-emergent adverse events are adverse events that occur after the start of study drug administration, through the Treatment Phase, and for 30 days following the last dose of study drug; any adverse event considered treatment-related regardless of the start date of the event; or any event that is present at baseline but worsens in severity or is subsequently considered drug-related by the investigator. The number and percent of subjects with treatment-emergent adverse events will be summarized according to intensity (NCI-CTCAE, Version 4.03) and drug relationship as well as categorized by System Organ Class and preferred term by treatment arm.

The verbatim terms used in the eCRF by investigators to identify adverse events will be coded using the Medical Dictionary for Regulatory Activities (MedDRA). Treatment-emergent adverse events are adverse events with onset during the Treatment Phase or that are a consequence of a pre-existing condition that has worsened since baseline. All reported adverse events will be included in the analysis. For each adverse event, the percentage of subjects who experience at least 1 occurrence of the given event will be summarized by treatment group. In addition, comparisons between treatment groups will be provided if appropriate.

Summaries, listings, datasets, or subject narratives may be provided, as appropriate, for those subjects who die, who discontinue treatment due to an adverse event, or who experience a severe or a serious adverse event.

Subjects with adverse events of special interest may be counted or listed.

Clinical Laboratory Tests

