1 INTRODUCTION

This study is designed to evaluate the efficacy and safety of imetelstat in transfusion-dependent subjects with low or intermediate-1 risk myelodysplastic syndrome (MDS) that is relapsed / refractory to erythropoiesis-stimulating agent (ESA) Treatment.

The purpose of the statistical analysis plan (SAP) is to lay out key elements including definitions and statistical methods for the planned analyses for the primary, secondary and exploratory endpoints. It describes the final reporting for study MDS3001 as per protocol amendment #7 dated as September 2, 2021. Safety data to be reviewed by the Data Monitoring Committee (DMC) periodically are specified in the DMC SAP, which is specifically prepared for DMC reviews.

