Part 2 is a double blind, randomized Phase 3 design to compare the efficacy of imetelstat with placebo. Approximately 170 subjects will be randomized in a 2:1 ratio to receive either imetelstat or placebo, respectively. Randomization will be stratified by prior RBC transfusion burden (≤ 6 or > 6 units RBC) and by International Prognostic Scoring System (IPSS) risk group (low risk versus intermediate-1 risk). Prior RBC transfusion burden is defined as the maximum number of RBC units transfused over an 8-week period during the 16 weeks prior to Cycle 1 Day 1 (C1D1) for subjects enrolled in Part 1 or the day of randomization for subjects enrolled in Part 2. In addition to the main study of Part 2, a separate Ventricular Repolarization substudy will enroll approximately 45 subjects to be randomized 2:1 to receive either imetelstat or placebo investigating the effects of imetelstat exposure on ventricular repolarization.

The randomization schedule will be prepared by an independent statistician not otherwise involved with this study and will be implemented within an interactive web response system (IWRS). Blinded treatment will be used for Part 2 to minimize the potential influence of treatment assignment knowledge on clinical decision making, and to reduce potential bias during data collection and evaluation of clinical endpoints, thus ensuring the robustness and integrity of the study. It is the intent that all subjects, investigators and study team members, except some required project roles, will remain blinded to treatment group assignment at least until the primary efficacy analysis (12 months after the last subject is randomized in the main study of Part 2) and the database is finalized. Subjects and investigators may be unblinded after primary efficacy analysis depending on the outcome of the primary efficacy analysis, potential DMC recommendations and/or interactions with health authorities. The study data sources with the potential to cause unblinding risks and the required project roles with appropriate restricted access to these data sources, and other measures to prevent the identification of study treatment(s) until all such opportunities for bias have passed, are described in a separate Blinding Maintenance Plan.

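### At the 24-month final analysis, adverse events are summarized by arm as crude percentages although time at risk will differ by arm after unblinding

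*SAP*

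**What the plan says.** **AE measure.** For each TEAE, SAP 4.10.1 reports "the percentage of subjects who experience" one or more occurrences, and repeats this for serious TEAEs and for TEAEs leading to discontinuation, death, dose modification or delay. SAP 4.3 states that Part 2 analyses are in general by treatment group. Protocol 11.10 is explicit: "the percentage of subjects who experience at least 1 occurrence of the given event will be summarized by treatment group". It then adds: "In addition, comparisons between treatment groups will be provided if appropriate". No method is given for those comparisons.

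**Window.** TEAEs run from first dose and "for 30 days following the last dose of study drug or until subsequent anti-cancer therapy if earlier". Events judged drug-related count whatever their start date.

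**Unblinding.** Protocol 5.2 says: "As of Protocol Amendment 8, subjects, investigators, and study team members will be unblinded after primary efficacy analysis". Protocol 3.2 lets imetelstat subjects continue at the investigator's discretion, and of the other arm says: "Subjects on placebo may discontinue treatment and enter the posttreatment follow-up phase of the study". Protocol 14.2 provides open-label imetelstat once the study is unblinded and names no further placebo supply for the main study (substudy subjects are treated separately). The note to Figure 3 in Protocol 3.1 sends placebo subjects to follow-up only in the Extension Phase.

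**Timing.** Protocol 11.4 puts the primary analysis at 12 months, and the final main-study analysis at 24 months, after the last randomization.

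**SAP basis.** The SAP is written "as per protocol amendment #7 dated as September 2, 2021" and leaves unblinding open: "Subjects and investigators may be unblinded after primary efficacy analysis depending on the outcome of the primary efficacy analysis".

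**The concern.** Because the TEAE window is tied to dosing, time at risk follows time on treatment. Up to unblinding, the planned schedule is the same in both arms. Afterwards the placebo window can close about 30 days later, while the imetelstat window can stay open for up to another year before the month-24 analysis. The percentage of subjects with at least one event rises with time at risk even when the event rate is the same. The month-24 table would therefore mix drug toxicity with length of observation.

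At stake is the reading of the longer-term safety data. Protocol 1.1.5.2.3 says that the long-term consequences of the abnormal liver findings under continued treatment are not known. A by-arm table in which one arm is watched longer can neither support nor dismiss a late signal. A second reason to separate the two periods is that, after unblinding, investigators judge drug-relatedness, which can by itself make an event treatment-emergent, knowing the treatment.

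**Working it through.** The documents state no figure for the AE comparison, so there is none to reproduce. The sample-size figure is not in dispute (150 subjects with the continuity correction gives 87.6% power, against the stated 88% or so).

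**Inputs from the documents.** Primary analysis at 12 and final analysis at 24 months after the last randomization (Protocol 11.4). TEAE tail of 30 days, taken as 1 month (SAP 4.10.1). Treatment duration: median 12 cycles as the planning figure (Protocol Table 12, footnote a) and median 8 cycles in the Part 1 target population (Protocol 1.1.5). With 28-day cycles, 12 cycles is 12 × 28 / 30.4375 = 11.04 months.

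**Assumptions, not in the documents.** The same constant AE hazard λ in both arms; 30% risk per 12 months on treatment; exponential discontinuation, equal in the arms; uniform enrollment over 0 to 36 months; all placebo subjects still on treatment stop at unblinding, taken as the 12-month point.

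**Hazard.** λ = −ln(0.70)/12 = 0.02972 per month, or 35.7 events per 100 patient-years.

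**Upper bound** (last-randomized subject, no other discontinuation):
- placebo, 12 + 1 = 13 months at risk: 1 − exp(−0.02972 × 13) = 32.0%
- imetelstat, 24 months at risk: 1 − exp(−0.02972 × 24) = 51.0%
- false excess: about 19 points

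**With discontinuation** (median 12 cycles, all randomized together). The discontinuation rate is δ = ln 2 / 11.04 = 0.0628 per month. If dosing ends at time c at the latest, the expected percentage is

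1 − e^(−λ) × { [δ/(δ+λ)] × [1 − e^(−(δ+λ)c)] + e^(−(δ+λ)c) }

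with c = 12 for placebo and c = 23 for imetelstat (23 + 1 = 24, the data cut). Here δ + λ = 0.0925 and δ/(δ+λ) = 0.679.
- placebo: 1 − 0.9707 × (0.679 × 0.670 + 0.330) = 23.8%
- imetelstat: 1 − 0.9707 × (0.679 × 0.881 + 0.119) = 30.4%
- false excess: 6.6 points; mean time at risk 9.4 and 13.2 months (ratio 1.40)

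**Other scenarios** (simulation, same hazard in both arms):

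| Enrollment (months) | Median cycles | On treatment at unblinding | Placebo | Imetelstat | False excess (points) |
|---|---|---|---|---|---|
| 0 | 12 | 47% | 23.8% | 30.4% | 6.6 |
| 0 | 8 | 32% | 20.9% | 24.8% | 3.9 |
| 12 | 12 | 33% | 27.9% | 31.9% | 4.0 |
| 24 | 12 | 24% | 30.0% | 32.6% | 2.6 |
| 36 | 12 | 19% | 31.1% | 33.0% | 1.9 |
| 36 | 8 | 9% | 25.1% | 25.9% | 0.8 |

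The range is 0.8 to 6.6 points. Over the same durations and enrollment periods it is 0.4 to 2.8 points at 10% annual AE risk and 0.8 to 7.8 points at 50%.

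**Exposure-adjusted rate.** Subjects with a first event divided by time at risk to first event or end of window gives λ in each arm: 35.7 per 100 patient-years in both, ratio 1.00 in every scenario.

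**The case against.** The strongest reply is that the comparison that decides benefit and risk is made at 12 months, before the planned unblinding. The summary of Amendment 7 describes that analysis as covering efficacy and safety with sufficient follow-up. This stands: the mechanism described here does not affect that table, and a comparison cut at unblinding will largely repeat it. What remains is the month-24 table, for which no such cut is specified.

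SAP 4.10.3 also plans time to onset and duration of Grade 3 or 4 thrombocytopenia, neutropenia and liver test abnormalities, persistent severe cytopenia, and shift tables by cycle. SAP 4.8 tabulates exposure. So crude percentages are not the only planned safety output. But these outputs do not cover AEs in general, and exposure is not used as an AE denominator. The permission in SAP 4.10.1 for additional summaries does not specify one.

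A reader might infer more than the documents support:
- *That placebo subjects must stop.* Protocol 3.2 only permits it. The supply and Extension Phase provisions make it likely.
- *That the arms have 12 and 24 months at risk, so that a hazard of 0.2 per year gives 18% versus 33%.* That holds only for the last-randomized subject with no other discontinuation, and it leaves out the 30-day tail. On the same basis, a 12-cycle median with simultaneous enrollment gives about 12.9% versus 17.9%.
- *That Extension Phase exposure inflates the comparison.* Protocol Section 11 gives that phase its own analysis at its end, and its objective concerns subjects receiving imetelstat.
- *That the table would hide toxicity.* This mechanism raises the imetelstat percentages.

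**Conclusion.** The point holds for the 24-month final main-study analysis. If placebo dosing largely ends at unblinding, crude TEAE percentages by arm will show an excess on imetelstat that is due to longer observation. With equal toxicity the false excess is about 1 to 7 points under the stated discontinuation and enrollment assumptions at 30% annual AE risk. About 19 points is the upper bound at that risk. The size depends mainly on how many subjects are still on treatment at unblinding (9% to 47% in the scenarios shown). The documents give neither that proportion nor the enrollment duration.

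The direction is against imetelstat. The practical harm is an uninterpretable late-safety table rather than a concealed risk. SAP version 2.0 (September 2022) predates Amendment 8 (December 2022), which explains why it does not address the asymmetry that the firm unblinding rule creates.

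**What to change.** 1. Update the SAP to Amendment 8, reconcile its conditional wording on unblinding with Protocol 3.2 and 5.2, and define the unblinding date to be used in analysis.
2. At the final analysis, restrict the between-arm AE comparison to events with onset up to that date. Report later imetelstat events as single-arm data.
3. Beside the crude percentages, add exposure-adjusted incidence (subjects with a first event per 100 patient-years at risk) for TEAEs, Grade 3 or higher TEAEs, serious TEAEs and AEs of interest.

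The cost is a SAP amendment and a few tables from dates already collected. The rates assume a roughly constant hazard. If toxicity is concentrated in early cycles, the longer imetelstat follow-up dilutes its rate and can flatter the drug. The rates should therefore not stand alone: show the crude percentages up to unblinding, or time-to-first-event curves, alongside them.
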